7.1.3 Laboratory Procedures/Assessments

Details regarding specific laboratory procedures/assessments to be performed in this trial are provided below.

7.1.3.1 Laboratory Safety Evaluations (Hematology, Chemistry and Urinalysis)

Laboratory tests for hematology, chemistry, urinalysis, and others are specified in the trial flow chart (Section 6) and section 12.7. The total amount of blood/tissue to be drawn/collected over the course of the trial (from pre- trial to post-trial visits), including approximate blood/tissue volumes drawn/collected by visit and by sample type per subject.

Laboratory tests for screening or entry into the Second Course Phase should be performed within 10 days prior to the first dose of treatment. After Cycle 1, pre-dose laboratory procedures can be conducted up to 72 hours prior to dosing. Results must be reviewed by the investigator or qualified designee and found to be acceptable prior to each dose of trial treatment.

7.2 Correlative Studies

Correlative Studies

Study-specific correlatives are outlined below. Remaining extra plasma and tissue after these studies are performed may be used for additional research studies focusing on molecular pathways of resistance to EGFR-directed therapy and additional immune markers.

A Study ID number will be assigned to each patient and will be used in sample coding instead of the name. The key linking the number with the patient identity and clinical outcomes will be kept by [name] and his research staff. This will be kept in a locked location.

7.2.1 EGFR-directed Correlative Studies

7.2.1.1 Plasma EGFR-mutant DNA

Molecular Studies: Blood

- Plasma DNA/RNA detection of EGFR and PD-L1

Prior to each cycle of treatment, two tubes of blood (1 for RNA and 1 for DNA) will be collected for EGFR and PD-L1 DNA and RNA quantification. Tubes will be provided in a collection kit from Liquid Genomics. The assay will be performed by Liquid Genomics, which has validated DNA and RNA assays for EGFR mutations and PD-L1 RNA levels. Please see Appendix 12.6 for tube collection and shipping instructions.

Please be sure to order kits from Liquid Genomics at the time of study activation (if not already available at the site).

7.2.1.2 EGFR-Activating Mutations and Mechanisms of Resistance to EGFR-TKIs on Biopsied Tumor Specimens

7.2.1.3 Standard-of-Care Baseline Biopsy

Biopsy of a patient's tumor upon progression with erlotinib to examine EGFR-resistance mechanisms such as EGFR T790M and rule out small cell histologic transformation is considered standard-of-care. The biopsied tissue performed at baseline will be sent to Foundation Medicine (for patients at UC Davis) or equivalent CLIA-certified assay for confirmation of EGFR-mutation status and determination of EGFR-T790M resistance mutation, following usual clinical procedures. If tissue permits, other mechanisms of resistance will be examined, prioritizing MET amplification, HER2 amplification, PIK3CA specific and pathway mutations, and MEK pathway mutations. (Biopsy must be performed within 60 days of consent).

7.2.2 Repeat Biopsies for EGFR-mutation Status and Immune Correlates

In all patients following consent, two biopsies will be attempted on study: one prior to initiation of study treatment and one after cycle #2 of treatment before initiation of cycle 3. This will be approximately week 5-6 on study (see study calendar). Patient consent for biopsies will be a study requirement.

Biopsies will be performed by a qualified professional and will be tailored to the available disease targets. Potential biopsies could include image-guided core biopsy, or limited surgical or pulmonary interventional biopsy. Image-guided tumor biopsies will be obtained with the help of the Interventional Radiology or Radiology team by a percutaneous approach or by the assistance of our surgical or pulmonary colleagues. Alternative biopsy techniques (e.g. transbronchial, skin punch biopsy) will be considered if indicated after discussion with the principal investigator. When a core biopsy is performed, it is preferred that a core biopsy system be used to obtain at least 3 core biopsies not less than 22 gauge in diameter and 1 cm in length (6 core biopsies is ideal).

If a site is deemed appropriate for biopsy with minimal risk to the participant by agreement between the investigators and biopsy team, a biopsy will be attempted. The use of imaging to facilitate biopsies will be decided by members of the Interventional Radiology or Radiology team and may include an ultrasound (US), a computer tomography (CT) scan, or a magnetic resonance imaging (MRI) scan. Should a CT scan be needed for biopsy, the number of scans for each procedure will be limited to the minimum number needed to safely obtain a biopsy. Tumor biopsies and local anesthesia will be administered only if they are considered to be of low risk to the participant, as determined by the investigators and/or the interventionist.

Tissue Study Requirements on Treatment Listed in Order of Priority

Test	Institution or commercial entity	Baseline Biopsy (slides)	On Treatment Biopsy (Prior to Cycle 3)
Standard-of-Care Genomic Testing in CLIA Certified Lab	Investigator Choice	Per SOC Guidelines	X
PD-L1 and QIF	Yale Translational Immuno-Oncology	5 slides minimum, 10 slides optimal	5 slides minimum, 10 slides optimal
Next Generation Sequencing with Mutational Load*	Broad Institute	10 slides minimum 20 slides optimal. (RNA later processing if available)	10 slides minimum, 20 slides optimal.

RPPA for on target EGFR-inhibition (EGFR, p-EGFR, pERK, ERK, pAKT, AKT), caspase 3 cleavage	Theranostics	3-5 unstained slides	3-5 unstained slides
* Companion blood draw in kit for germline DNA comparison			

7.2.2.1 Standard-of-Care Genomic Testing

Tumor biopsy at baseline will be sent for standard molecular testing at a CLIA-certified lab for confirmation of EGFR activating mutation and to detect the presence or absence of an EGFR-T790M mutation as well as other resistance mechanisms to EGFR-TKI. When possible, the post-TKI specimen will be compared to the diagnostic block to identify treatment-induced differences in molecular profiles.

7.2.2.2 PD-L1 and Evaluation of TILS

The PD-L1 immunohistochemistry will be performed in 3-5 μm -thick histology preparations obtained from conventional biopsy formalin-fixed, paraffin-embedded (FFPE) tissue samples. The tumor PD-L1 protein will be tested using the FDA-approved Dako 22C3 assay using chromogenic immunohistochemistry in the Yale Pathology Labs or UC Davis under CLIA laboratory conditions. The scoring procedure will include the determination of the percentage of positive cells in the tumor by a surgical pathologist using bright field microscopy. The score will be semi-quantitative and determined based on the percentage of positive cells.

The level of major TIL subtypes, TIL activation/proliferation and expression of major immune inhibitory receptors will be evaluated using multiplexed quantitative immunofluorescence (QIF) performed in 3-5 μm -thick histology preparations obtained from formalin-fixed, paraffin-embedded (FFPE) tissue samples, as previously reported (Schalper KA, Brown J, Carvajal-Hausdorf D, McLaughlin J, Velcheti V, Syrigos KN, et al. Objective measurement and clinical significance of TILs in non-small cell lung cancer. *J Natl Cancer Inst.* 2015;107.). We will perform three multiplexed QIF panels containing the following markers: Panel #1: DAPI/CD4/CD8/CD20; Panel #2: DAPI/CD3/Granzyme-B/Ki-67; and Panel #3: DAPI/CD3/PD-1/TIM-3/LAG-3. The Yale group has already performed validation of the antibodies and combined these markers into multiplexed QIF panels. Simultaneous measurements of the targets will be performed using multispectral imaging and the AQUA® method providing continuous fluorescence marker scores. Eventually, quantification of positive cells for each marker will also be performed using the Vectra multispectral imaging platform with the cell phenotyping tool of the InForm® software; and reported as cell density (number of cells/area unit). See section 7.2.4 for processing and shipping information for the PD-L1 and QIF samples.

7.2.2.3 Next-Generation Sequencing with Mutational Load and Reverse-phase protein arrays (RPPA)

Next-Generation Sequencing (DNA and RNA - if sufficient tissue available) of the Stand Up 2 Cancer (SU2C) Customized Gene Panel which is the standard for the Lung Cancer dream team with a focus on resistance mechanisms to EGFR-TKI and quantifying mutational load will be performed at the Broad Institute. This will be performed at baseline biopsy unless tissue amount is inadequate where it will be performed on the on-treatment biopsy. When requested, the Broad Institute Samples lab will ship sample collection kits to research site. A companion blood collection tube will also be provided and should be collected at baseline for germline mutation testing.

Kits are specific for Material Type collected

- i. Labels – FFPE or Frozen Tumors
- ii. Labels – Blood or Buffy Coat Samples
- iii. Matrix Kits – DNA or RNA analytes

1. Researcher fill kit & provides Sample Kit Metadata spreadsheet (example provided).
2. Kits are shipped back to the Broad Institute Samples lab per instructions provided in the kits. (See Attached Documents). Specimens should be coded with a unique identifier (ie., Institution, Clinical Trial Number, patient number and biopsy number in sequence (ie. for patient 1, UCD250-001-01 (baseline biopsy), UCD250-001-02 (on-treatment biopsy), UCD250-001-03 (post progression biopsy).

Sample Processing & Data Generation will proceed. (Turnaround Time is expected to be 5-6 weeks for Exome runs). RNA sequencing will be batched so timeline will be more variable.

7.2.3 Immunology Correlates

Immune correlates will be performed by Yale University Translational Immuno-Oncology or the Human Immune Monitoring Core (HIMC) at UC Davis as outlined below.

PD-L1 expression will be assayed using Merck's proprietary 22C3 antibody that is FDA approved as a companion diagnostic for pembrolizumab for quantifying PD-L1 expression for MK-3475 trials in NSCLC and melanoma including Garon, Edward B. Naiyer A. Rizvi. **"Pembrolizumab for the Treatment of Non-Small-Cell Lung Cancer."** nejm.org. The New England Journal of Medicine. April 19, 2015.

7.2.3.1 Biopsied tumor for PD-L1 Quantification

PD-L1 expression by immunohistochemistry at baseline and in repeat biopsy specimens to assess for changes in PD-L1 expression in response to treatment will be conducted by UC Davis or Yale Translational Immuno-Oncology using the FDA approved DAKO 22C3

antibody and by quantitative IHC.

7.2.3.2 Biopsied tumor for Tumor Infiltrating Lymphocytes and Subsets and RT-PCR for Immune Markers

In baseline and on treatment biopsies, the HIMC at UC Davis or Yale University Immunology Core will quantify changes in tumor infiltrating lymphocytes and immune subsets using IHC for T-cell subsets that include CD4, CD8, and Foxp3. Real time-PCR for immune markers (if tissue size permits) including CD3, PD-1, GranzB, Perforin, IL-2, IFNg, Tim3, LAG3, CTLA-4, Foxp3 will be performed if adequate tissue is available.

7.2.4 EGFR & Immunology Biopsy Processing

Tumor tissue obtained at each biopsy time point will be collected by a representative of the study team. At the first biopsy, one of the cores will be submitted directly to Pathology for clinical interpretation and report as well as standard of care molecular studies. The remaining cores will be delivered to UC Davis Research Pathology, [name] (*or corresponding local research lab at other trial sites*) and divided into 2 components.

At least two core biopsies not less than 22 gauge in diameter and 1cm in length or tissue the equivalent of core biopsies sufficient to generate at least 20 cut slides should be paraffin embedded and stored in research pathology until ready for processing and shipping. Ideally, 6 cores per biopsy timepoint should be obtained. At the first timepoint 2 cores should be used for histologic confirmation and standard molecular testing. 2 cores should be paraffin embedded for IHC of PD-L1 and other markers of the tumor immune microenvironment. At UC Davis, this FFPE specimen may also be stored in the laboratory of [name] or the UC Davis HIMC for storage until sent for further testing.

If available, two additional cores should be immediately stored in 2ml of RNAlater solution (Life Technologies) (the tissue portion should be processed into pieces, each less than 0.5cm³) for comprehensive DNA/RNA sequencing at the Broad Institute. The Samples in RNAlater solution should be kept refrigerated until processed at HIMC. This should be delivered to the Human Immune Monitoring Core with the contact information listed below. If not enough cores are obtained DNA/RNA sequencing can be sent of the initial FFPE tissue

Specimens in RNA Later should be shipped on cool packs (Monday – Thursday only) to:

Human Immune Monitoring Core ([name] Laboratory)
Department of Dermatology
UC Davis School of Medicine
[name]
[name]

LAB: [contact]

Tissue from the second biopsy timepoint will be divided into the 2 research components with the procedures outlined above. Component 1: at least 2 cores or enough tissue for 20 cut slides as specified for initial biopsy for FFPE for PD-L1 and additional IHC quantification by UC Davis or Yale and 2: remaining cores in RNA later solution then FFPE for DNA/RNA sequencing. **(If no cores were available for processing with RNA later in the initial biopsy, the repeat biopsy should all go through FFPE and not through an RNA later step).** A research H&E slide will also be generated and reviewed by a research pathologist to confirm presence of tumor.

If there is limited tissue for the baseline biopsy priority should be given to pathologic assessment and molecular testing at Response Genetics per standard of care and then PD-L1 testing by the central vendor. For the repeat biopsy priority should be given for PD-L1 and additional IHC testing by the central vendor and UC Davis HIMC.

RPPA will be performed at Theranostics using their established procedures for FFPE samples under their CAP-accredited CLIA laboratory. Our previous experience with this resource is that, for phosphorylation states of intracellular signaling molecules, the assay is highly quantitative and correlates with Western blotting analysis conducted at UC Davis. The following analytes will be performed, listed in order of priority (although measured simultaneously): pEGFR, totalEGFR, pERK, totalERK, pAKT, totalAKT, caspase 3 cleavage.

7.2.4.1 Immunohistochemistry and Quantitative Immunofluorescence

Immunohistochemistry and Quantitative Immunofluorescence: Staining for PD-L1, relevant immunoproteins and tumor infiltrating immune cells will be performed by the SU2C Immune Core at Yale University as outlined below. Tissue samples will be collected from participants who have been properly consented and who have agreed to participate in the research study. Tumor tissues are optimally suitable for IHC/QIF studies if fixed in 10% neutral buffered formalin (NBF) for 16-24 hours **and processed into paraffin blocks using clinical-grade pathology laboratory conditions.**

1. Select the tumor block and obtain one Hematoxylin & Eosin (H&E) stained slide for review by site pathologist to confirm diagnosis and ensure presence of tumor cells. For *in situ* analyses, there is no lower limit in the amount of tumor cell content.
 - a. Samples with few tumor cells (<100-200 cells) may be insufficient for PD-L1 immunostaining but should still be submitted for the QIF studies of TILs and other stromal markers.
3. If pathologist review is not possible or available at the site, the H&E slides or a digital version may be sent directly to Yale Pathology for initial assessment.
3. Obtain 5 additional serial 4-5 μ m thick sections from the reviewed paraffin block and place each section in a positively-charged glass histology slide. Tissues should be cut and

processed using conventional, clinical-grade in-house histology protocols. Paraffin dipping of slides after sectioning is not recommended.

4. Collect 5 freshly cut (<5 days) unstained serial section slides from each case, label each preparation using the SU2C coding system and place them in a conventional plastic histology slidebox. Make sure slides are in a firm position to avoid damage during transportation and cover with paper towel prior to packing to prevent movement within the box. If possible, also include the sectioning order on the label for each slide.

a. Whenever feasible, blocks should be processed in batches, and shipped together within a 5-day period after sectioning.

5. Include H&E stained preparation together with the 5 unstained sections in the slidebox. This slide will be digitalized and become available for review within the SU2C group. Specimens should be coded with a unique identifier (ie. institution, trial number, patient number and biopsy number in sequence (ie. for UC Davis patient 1, UCD250-001-01 (baseline biopsy), UCD250-001-02 (on-treatment biopsy), UCD250-001-03 (post progression biopsy)).

6. Seal the slidebox using Parafilm and/or a plastic envelope and wrap with bubble wrap prior to shipping. Include detailed sender information (with email) and ship using overnight service to:

Attention to: [name] ([contact]).

Backup contact should [name] be out is [name] ([contact])

Address: [name]
Department of Pathology
Yale School of Medicine
[name]
[name]

Phone 1: [contact]

Phone 2: [contact]

A confirmation of sample reception will be sent via email to the sender within 72 hours.

7. Slides will be stained for IHC and the QIF panels within 5 working days from reception in the lab or stored in appropriately until use and batched to accommodate projects in single experimental runs (whenever possible).

8. Results of the analyzed markers will be provided as continuous scores using fluorescence intensity scores and/or phenotype cell counts. The turnaround time will depend on the amount of slides and project volume.

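### Slide codes reveal which biopsy is baseline and which is on treatment, PD-L1 reading is not stated to be masked, and a patient's two biopsies need not share a staining run or laboratory, so within-patient PD-L1 change is open to reader, run and laboratory effects

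*Combined protocol and SAP*

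**What the plan says.** **Coding.** Section 7.2.4.1 gives the specimen code as institution, trial number, patient number and biopsy number in order, with this example: "for UC Davis patient 1, UCD250-001-01 (baseline biopsy), UCD250-001-02 (on-treatment biopsy), UCD250-001-03 (post progression biopsy". Section 7.2.2.3 uses the same scheme. Item 4 of 7.2.4.1 puts the code on the slides themselves: "label each preparation using the SU2C coding system and place them in a conventional plastic histology slidebox".

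**Reading.** Section 7.2.2.2 scores 22C3 PD-L1 by "determination of the percentage of positive cells in the tumor by a surgical pathologist using bright field microscopy" and adds: "The score will be semi-quantitative and determined based on the percentage of positive cells". No section says that the reader is unaware of time point, patient or cohort, or that slides are re-coded before reading.

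**Staining time.** Item 7 of 7.2.4.1 reads: "Slides will be stained for IHC and the QIF panels within 5 working days from reception in the lab or stored". The stored slides are then batched by project into single runs, but only where this can be arranged. Footnote 10 of the flow chart (Section 6.1) sets the repeat biopsy before cycle 3, at day 42 with a window of minus 7 days.

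**Laboratory.** Section 7.2.2.2 places the 22C3 assay "in the Yale Pathology Labs or UC Davis under CLIA laboratory conditions". Section 7.2.3.1 says the baseline and repeat PD-L1 assays "will be conducted by UC Davis or Yale Translational Immuno-Oncology", and the text on the second biopsy in 7.2.4 also allows either laboratory. The tissue table in 7.2.2 and the opening of 7.2.4.1 name Yale only. For limited baseline tissue, 7.2.4 refers to "PD-L1 testing by the central vendor" without identifying the vendor.

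**Use.** PD-L1 change is Exploratory Objective 1 (3.3), a focus of the arm A versus arm B comparison (8.2), and one of the measures in the pick-the-winner step (8.1), alongside toxicity, response rate and PFS.

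**The concern.** The quantity of interest is a difference between two readings on the same patient. Anything that moves the second reading relative to the first, other than biology, goes into the estimate. Three routes are open. A reader who can see the suffix may score the on-treatment slide with an expectation in mind. Two slides stained weeks apart can differ because of the run. Two slides stained at different laboratories can differ because of the laboratory.

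The first route matters most for the 22C3 percentage, because it is a visual estimate. The other two also affect the quantitative assays. None of these effects can be separated from a treatment effect once the slides have been read, so they have to be prevented in slide handling. At stake is whether an apparent rise or fall in PD-L1 within a cohort is real and, more weakly, what PD-L1 contributes to the choice of schedule.

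**Working it through.** **The plan's own figures.** The plan gives no calculation for PD-L1. Its one design calculation concerns response: with 10 patients and a threshold of 3 responders, it states 7% at a true rate of 10% and 83% at 40%. The exact binomial gives 0.0702 and 0.8327, so both reproduce. Neither bears on this point.

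**Can a pair share a run under the stated rules?** If slides are stained within 5 working days of receipt and each biopsy is sent when taken, the baseline slides are stained around the start of treatment. The repeat biopsy is taken 35 to 42 days after first dose, so the pair falls in two runs. If slides are stored and the project is batched into one run, the pair shares it. The text permits both routes and requires neither.

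**Size of a within-cohort bias.**
- Pairs: n = 10, the planned size of one expansion cohort (2.1), assuming every patient has both biopsies.
- SD of within-patient change: assumed 15, 20 or 35 percentage points. The documents give none.
- Consistent shift of the on-treatment reading relative to baseline: assumed 5 or 10 points. The documents give none.
- Test: two-sided 5% paired t-test, 9 degrees of freedom, critical value 2.262. The plan specifies no test, so this serves only as a yardstick.

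With no true change, the t statistic is noncentral with parameter shift / (SD / √n). For example, at SD 20 and a shift of 10: 10 / (20 / √10) = 10 / 6.32 = 1.58. The false-positive rate is the probability that |t| exceeds 2.262.

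| SD | Shift | Noncentrality | False-positive rate |
|---|---|---|---|
| 15 | 5 | 1.05 | 15.7% |
| 15 | 10 | 2.11 | 46.9% |
| 20 | 5 | 0.79 | 10.9% |
| 20 | 10 | 1.58 | 29.3% |
| 35 | 5 | 0.45 | 6.9% |
| 35 | 10 | 0.90 | 12.8% |

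**What reaches A versus B.** Let the shift between a patient's two slides average s_A in cohort A and s_B in cohort B. The bias in the difference of mean changes is s_A − s_B.
- Reader bias of equal size in both cohorts: s_A = s_B, so the bias is zero.
- A new laboratory or reagent lot that adds a constant to both slides of every later patient: the constant drops out of each patient's change, so the bias is zero.
- A switch that falls between the two biopsies of some patients only: if 2 of 10 pairs in one cohort straddle a shift of 5 to 10 points, the cohort mean moves by 2/10 × 5 = 1 to 2/10 × 10 = 2 points. At SD 20, treating this as a shift in the mean, the two-sample false-positive rate is about 5.1% to 5.5%.
- Every pair of one cohort shifted in the same direction and none of the other: at SD 20 the two-sample rate is 8.3% (5 points) or 18.5% (10 points). This is an extreme case.

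**The case against.** **The analysis is exploratory.** Section 8.2 is descriptive and calls any p-values hypothesis-generating, and PD-L1 change is one unweighted criterion among several. This stands, and it limits the severity. It does not remove the point, because 8.1 uses the result in choosing a schedule.

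**Safeguards exist.** A project batched into one run contains both biopsies of every pair. Section 7.2.4.1 also asks for blocks to be processed and shipped in batches where feasible, and quantitative assays with continuous scores accompany 22C3. Yale is the only laboratory in the operating procedure, and 4.4.3.2 presents UC Davis as a possible addition. All of this lowers the risk. But the batching is optional, continuous scoring does not remove run or laboratory effects, and split pairs remain possible through inconsistent wording rather than by design. The study ID in 7.2 hides the patient's identity, not the time point.

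**Unpaired runs mostly add noise.** This is right where shifts vary in sign from pair to pair. The table above applies only to a consistent shift. Unmasked reading is the likelier source of one.

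**Stronger readings that the documents do not support.** A reader might infer that, because cohort B enrols after cohort A is complete, any change of laboratory or lot falls on the A-versus-B contrast. An additive change that affects both of a patient's slides cancels in the within-patient change. A reader might also infer that the patient number reveals the cohort. No section says that numbers follow enrolment order. The code begins with the institution, so numbering may be by site, and de-escalation patients come first.

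**Conclusion.** The point holds for within-patient change. The slides disclose the time point, masking is not stated, and nothing requires a patient's pair to share a run or a laboratory. On the assumed values, a consistent shift of 5 to 10 points would raise a nominal 5% within-cohort error rate to between 7% and 47%, depending mainly on the SD of change. These figures show sensitivity and do not predict a bias: SD, shift and test are all assumptions, and ten complete pairs is the best case for data yield.

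The A-versus-B comparison is biased only if the shift between a patient's two slides differs by cohort. The documents leave that possible but do not make it likely, so it would go too far to say that the schedule choice is biased by the coding alone. Severity is low to moderate. The change is still worth making because it is cheap and the effect cannot be repaired in the analysis.

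**What to change.** 1. The study team issues random slide codes, which sites apply to the unstained slides and the accompanying H&E slide before shipping. The team keeps the key with the one already described in 7.2, and whoever scores PD-L1 has no access to it. Coding at the site suits slides that go straight from sites to Yale.
2. Keep both blocks. Cut, stain and score each patient's pair together, in one run, at one named laboratory, with the reader unaware of time point and cohort. Cutting the pair together also fits the freshly-cut requirement in item 4 of 7.2.4.1.
3. In item 7 of 7.2.4.1, make the single-run wording firm for pairs.
4. Reconcile the PD-L1 laboratory named in 7.2.2 (table), 7.2.2.2, 7.2.3.1, 7.2.4 and 7.2.4.1, and identify or delete the central vendor.
5. Code slides from patients with no repeat biopsy in the same way and include them in a later run, so that an unpaired slide does not stand out.

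**Cost.** A relabelling step, and a baseline PD-L1 result that waits for the repeat biopsy: 35 to 42 days after first dose, and longer from tissue collection where archival tissue is used, since that may be up to 60 days old at consent. Entry requires adequate tissue but no PD-L1 cut-off, so enrolment is unaffected. No extra biopsy or reader is needed.
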